6.5.7.2 Molecular Evaluation

The primary endpoint of the study is to explore and define the molecular alterations that may occur following darolutamide administration through comparisons of BC tissue before and after short-term exposure to darolutamide.

At least, the following markers will be assessed on the collected samples. In all experiments, appropriate positive and negative controls will be included.

- AR
- ER
- PgR
- HER2
- ki67
- Cytokeratins 5 and 6

Tissue microarrays will be developed from all tumor specimens. Other *in situ* assays for activated downstream signaling molecules will be performed using tissue sections and/or tissue microarrays. Promising candidate genes obtained from the microarray analysis will be validated using the frozen

tissue arrays generated above and using appropriate probes (i.e. antibodies, if available, or nucleic acid probes).

Additional assays in example but not limited to Reverse Phase Protein Analysis (RPPA), sequenciation of the RNA, immunohistochemistry (IHC) etc. may be performed based on the molecular analysis finding and/or in the future as new technology and data become available.

6.5.8 Other Procedures/Assessments

In addition to the protocol-required assessments, the Investigator may perform any clinically indicated test and procedure according to SoC (e.g. coagulation test prior to surgery, etc.) although these will not be collected in the eCRF.

7. SAFETY MONITORING

7.1 Definitions

7.1.1 Period of Observation

At each visit and any contact during the study and follow-up period, the Investigator or designee will inquire about the occurrence of AEs (and corresponding medications administered) and will document them in the eCRF.

For the purposes of this study, the period of observation for SAEs and AEs extends from the time the patient signs the PICF until the EOS, except for patients that are experiencing AEs or SAEs related to darolutamide ongoing at the time of EoS visit. In such cases, these events will be monitored beyond the EoS visit as clinically indicated until (a) the events have resolved or (b) the events have reached a status which, in the Investigator's opinion, is unlikely to resolve due to the nature of the condition and/or the patient's underlying disease.

The Investigator or designee will report the AEs/SAEs in the eCRF (and, if applicable, to TRIO Safety Department) when required as per the table below:

Table 3: Reporting Period of AEs/SAEs

Study period	AEs (non-serious)	SAEs
From PICF to 1 st intake	Only if related to study participation	All (regardless of relationship)
From 1 st intake until EoS visit	All (regardless of relationship)	All (regardless of relationship)
After the EoS visit	Only if related to protocol treatment	Only if related to protocol treatment

7.1.2 Adverse Event

An AE is defined as any untoward medical occurrence, including an exacerbation of a pre-existing condition, in a patient in a clinical investigation who received a pharmaceutical product. The event does not necessarily have to have a causal relationship with this treatment.

Worsening of pre-existing conditions: any pre-existing condition present at baseline, which remains unchanged during the trial, does not need to be recorded as an AE.

Any worsening of any pre-existing baseline condition should be reported as an AE in the eCRF. Examples of worsening of a preexisting condition that should be recorded as an AE are given below:

- Worsening of condition meets the criteria for an AE or SAE
- Action is taken with the investigational drug (e.g. dose is reduced or treatment is discontinued)
- Treatment is required (concomitant medication is added or changed)
- The Investigator believes a patient has shown a clear deterioration from baseline symptoms

Expected fluctuations or expected deterioration of the BC (symptoms of disease progression) should not be recorded as an AE.

Changes in vital signs, physical examination and laboratory test results: these will only be recorded as an AE in the eCRF if they are judged clinically relevant by the Investigator or led to protocol treatment modifications (dose delay or dose reduction).

Surgical procedures: these are not AEs *per se*; they are therapeutic measures for conditions that require surgery. The condition for which the surgery is required may be an AE. Planned surgical measures permitted by the clinical study protocol and the condition(s) leading to these measures are not AEs.

Worsening of a sign or symptom of the condition under treatment: these situations (i.e. BC) should not be recorded as AEs.

7.1.3 Serious Adverse Events

A SAE is one that at any dose:

- Results in death
- Is life-threatening¹
- Requires inpatient hospitalization or prolongation of existing hospitalization
- Results in persistent or significant disability or incapacity²
- Is a congenital anomaly or birth defect
- Is an important medical event³

¹ “Life-threatening” means that the patient was at immediate risk of death at the time of the SAE; it does not refer to a SAE that hypothetically might have caused death if it were more severe.

² “Persistent or significant disability or incapacity” means that there is a substantial disruption of a person’s ability to carry out normal life functions.

³ Medical and scientific judgment should be exercised in deciding whether expedited reporting is appropriate in situations where none of the outcomes listed above occurred. Important medical events that may not be immediately life-threatening or result in death or hospitalization but may jeopardize the patient or may require intervention to prevent one of the other outcomes listed in the definition above should also usually be considered serious. Examples of such events include allergic bronchospasm requiring intensive treatment in an emergency room or at home, blood dyscrasias or convulsions that do not result in inpatient hospitalization, the development of drug dependency or drug abuse, etc.

7.1.3.1 Disease-related Events

An event that is part of the natural course of the disease under study (i.e. breast cancer) does not need to be reported as an SAE.

However, if the Investigator considers that there was a causal relationship between treatment with investigational product or protocol design/procedures and a disease progression, then this must be reported as an SAE. Any new primary cancer must be reported as an SAE.

7.1.3.2 Planned or Administrative Hospitalization

Patients may be hospitalized for administrative or social reasons during the trial (e.g. long distance from home to site, etc). These and other hospitalizations planned up to enrollment do not need to be reported as an SAE but should be properly documented in the source data.

7.1.4 Unexpected Adverse Event

The Darolutamide IB provides an overview of the AEs reported across each clinical trial.

Any SAE assessed as related to darolutamide but not presented in the IB section 8.6 Undesirable effects will be documented by TRIO as a suspected unexpected serious adverse reaction (SUSAR) and will be submitted according to applicable local regulations.

7.2 Performing Adverse Event Assessment

7.2.1 Collection of Adverse Event Information

The following information will be collected in the eCRF: Description of event (a single medical condition and not a collection of signs/symptoms), start/stop dates, worst grade experienced (severity/intensity), seriousness, action taken on protocol treatment and relationship to protocol treatment.

Intensity of AE: The intensity of AEs will be classified and recorded according to the NCI CTCAE version 4.03 in the eCRF, or according to the grading defined in section 5.4.1 if the AE is not specifically listed in NCI CTCAE.

All adverse clinical experiences, whether observed by the Investigator or reported by the patient, must be recorded, with details about the duration and intensity of each episode, the action taken with respect to the test drug (refer to section 5.4.2 for recommendations on dose modifications), and the patient's outcome. The Investigator must evaluate each adverse experience for its relationship to the test drug and for its seriousness.

The Investigator must appraise all abnormal laboratory results for their clinical significance. If any abnormal laboratory result is considered clinically significant, the Investigator must provide details about the action taken with respect to the protocol treatments and about the patient's outcome.

7.2.2 Assessment of Causality

Medical judgment should be used to determine the relationship, considering all relevant factors, including pattern of reaction, temporal relationship, de-challenge or re-challenge, confounding factors such as concomitant medication, concomitant diseases and relevant history. Assessment of causal relationship must be recorded for each adverse event.

Relationship to study drugs will be reported as either "Yes" or "No".

- Yes: there is a reasonable causal relationship between the IMP administered and the AE.
- No: there is no reasonable causal relationship between the IMP administered and the AE.

7.3 Reporting of Serious Adverse Events and Pregnancies

7.3.1 Reporting of Serious Adverse Events and Pregnancies from the sites to TRIO

SAEs and pregnancies will be reported within 24 hours of awareness by completing and emailing or faxing the SAE Reporting Form to TRIO Drug Safety Unit.

TRIO Drug Safety Unit contact information:

- Email: [contact]
- [contact]

Table 4: SAE and Pregnancies Reporting Timelines

Type of Event	Initial Reports		Follow-up Information	
	Time Frame	Documents	Time Frame	Documents
All SAEs	Within 24 h of awareness	SAE reporting form	Within 24 h of awareness	SAE reporting form
Pregnancy	Within 24 h of awareness	Pregnancy reporting form	Within 24 h of awareness	Pregnancy reporting form

7.3.2 SAE information Provided by TRIO to the Manufacturer

TRIO will report all SAEs and pregnancies as well as follow up information for these events to Bayer by email or other secure method within 24 hours of awareness.

7.4 Management of Specific Cases

7.4.1 Medication Errors

In the event of a medication error, the patient should be observed closely for signs of toxicity. Medication errors include the accidental or intentional use of darolutamide in a daily dose greater than the protocol-specified daily dose. Appropriate supportive treatment should be provided if clinically indicated. In case of toxicity derived from the medication error, dose modification recommendations from section 5.4.2 should be followed.

The highest darolutamide dose administered in clinical trials is 1,800 mg daily, with no maximum tolerated dose achieved and no dose-limiting toxicity experienced by patients.

If an AE is associated with (“results from”) a medication error, the corresponding AE should be reported as SAE, even if no other seriousness criteria are met.

In cases of a medication error without any associated AE, the medication error should be reported as a non-serious AE, using terminology like “accidental or intentional overdose without adverse effect”, “medication error without adverse effect” or similar.

7.4.2 Pregnancy

Should a pregnancy occur, the Investigator must discontinue treatment immediately, capture any drug exposure during pregnancy, report the pregnancy through the Pregnancy Reporting Form and follow the pregnancy until outcome is known. Information related to outcome of the pregnancy, delivery, postpartum recovery and the clinical condition of the offspring during the neonatal period must also be collected.

Pregnancy is not automatically considered as a SAE, however, it must be reported following SAE timeline as detailed in section 7.3.

A SAE report must be forwarded to the TRIO if the outcome of the pregnancy results in an abortion/miscarriage or the occurrence of any other SAE(s).

7.5 Reporting to Ethics Committees, Regulatory Authorities and other Investigators

Prompt notification of SAEs by the Investigator to TRIO is essential so that legal obligations and ethical responsibilities towards the safety of patients are met.

TRIO will comply with local regulatory requirements relating to safety reporting to the regulatory authorities, IRB/IEC and Investigators.

TRIO will report SAEs and related safety information to the FDA as per the definitions and recommendations in 21 CFR 312 and per the FDA guidance for Industry and Investigators (available at <http://www.fda.gov/downloads/Drugs/.../Guidances/UCM227351.pdf>).

Investigator safety reports are prepared for SUSARs according to local regulatory requirements and are forwarded to Investigators as necessary.

An Investigator who receives an Investigator safety report describing a SAE(s) or other specific safety information (e.g., summary or listing of SAEs) from TRIO will file it with the IB and will notify the IRB/IEC, if appropriate according to local requirements.

8. STATISTICAL CONSIDERATIONS

8.1 Study Populations

- Intention-to-treat (ITT) Population: The ITT population includes all patients who are enrolled in the study regardless of whether they have been treated or not.
- Safety Population: The Safety population includes all patients who have taken at least one tablet of darolutamide.
- Evaluable population: Includes all patients who satisfied all criteria in section 8.5.

8.2 Demographics and Baseline Characteristics

Demographics and baseline characteristics data will be listed and summarized by each BC subtype using the ITT population.

8.3 Protocol Treatment

Duration of treatment, duration of exposure, cumulative dose and relative dose intensity will be summarized by each BC subtype using the Safety population. The patients with dose modifications will also be presented, along with reasons for the dose change.

8.4 Safety Evaluation

The assessment of safety will be made on the Safety population and will be based mainly on the frequency of AEs. The latest version of the Medical Dictionary for Regulatory Activities (MedDRA) will be used to code all AEs to a preferred term and system organ class. AEs will be graded using the NCI CTCAE v4.03 or according to the applicable grading if the AE is not specifically listed in NCI CTCAE. Patient's incidence of AEs will be tabulated by system organ class, preferred term and toxicity grade for each BC subtype. AEs leading to death or drug discontinuation, drug related and SAEs will also be summarized.

Detailed listings for all AEs will also be provided.

Laboratory parameters: these will be summarized at baseline, along visits and at the EoS visit by each BC subtype, graded according to the NCI CTCAE v4.03. Tables of shifts in toxicity will also be provided.

Other Safety Data: ECOG will be summarized at baseline, along visits and at the EoS visit by BC subtype. Tables of shifts in toxicity will also be provided when applicable.

8.5 Sample Size

The primary objective of this trial is to evaluate molecular alterations occurring in BC tissue following short-term darolutamide administration.

Up to 60 patients (minimum of 8 but up to 20 patients in each BC subtype: triple-negative, HR+/HER2 negative, HER2 positive) will be required for the performance of the molecular studies and possible hypothesis generation.

A patient will be considered evaluable if the following criteria are met:

- Minimum duration of treatment with darolutamide is of 14 days, with a minimum of 10 consecutive days of treatment prior to the definitive BC surgery/pre-NAST biopsy.
- Mandatory tumor tissue is collected at screening and at BC surgery/pre-NAST biopsy according to the protocol and submitted to the central laboratory.
- Adequacy for molecular assessment of the tumor tissue collected before and after the protocol treatment initiation. The adequacy will be evaluated by the central laboratory.

Assessment of patient evaliability, safety and distribution of patients with respect to hormone receptor status and HER2 status will be performed by the SSC at given time points depending on the recruitment, for example once 20, around 35 and once all patients have been enrolled and undergone the EoS per protocol. This will allow SSC to ascertain that the appropriate number of evaluable patients is being accrued, that more or less patients may be required, or in the extreme case, that accrual should close if the patient evaliability rate is very low and/or safety concerns arise.

The SSC will define the evaliability of patients that discontinue treatment more than 3 days before BC surgery/pre-NAST biopsy; molecular analyses may be taken into consideration for the decision about the evaliability of such patients.

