	Up to 60 patients (a minimum of 8 evaluable patients and up to 20 patients in each breast cancer subtype: triple-negative, HR+/HER2 negative, HER2 positive) will be required for the performance of the molecular studies and possible hypothesis generation. A patient will be considered evaluable if the following criteria are met: 
▪ Minimum duration of treatment with darolutamide is of 14 days, with a minimum of 10 consecutive days of treatment prior to the definitive BC surgery/pre-NAST biopsy.▪ Mandatory tumor tissue is collected at screening and at BC surgery/pre-NAST biopsy according to the protocol and submitted to the central lab.▪ Adequacy for molecular assessment of the tumor tissue collected before and after the protocol treatment initiation. The adequacy will be evaluated by the central lab. Assessment of patient evalability, safety and distribution of patients with respect to hormone receptor status and HER2 status will be performed by the Study Steering Committee (SSC) at given time points depending on the recruitment, primarily planned once 20, around 35 and once all patients have been enrolled and undergone the EoS per protocol. This will allow for the SSC to ascertain that the appropriate number of evaluable patients is being accrued, that more or less patients may be required, or in the extreme case, that accrual should close if the patient evalability rate is very low and/or safety concerns arise. The SSC will define the evalability of patients that discontinue treatment more than 3 days before surgery: molecular analyses may be taken into consideration for the decision about the evalability of such patients.						
Study Populations	Study Populations 
▪ Intention-to-treat (ITT) Population: the ITT population includes all patients who are enrolled in the study regardless of whether they have been treated or not.▪ Safety Population: the Safety population includes all patients who have taken at least one						

	tablet of darolutamide.
--	-------------------------

- Evaluable population: includes all patients who are considered evaluable per protocol.

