8.6 Molecular Analyses

The molecular analyses will be performed on the evaluable population. Descriptive statistics will be used to compare the pre-and post molecular findings.

A correlation analysis between the molecular alterations from the baseline tumor samples and the sample collected following administration of darolutamide, during the definitive BC surgery/pre-NAST biopsy will be conducted.

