9. ADMINISTRATIVE, ETHICAL AND REGULATORY STANDARDS

9.1 Steering Committee

The SSC of the trial will be composed of the study Chair(s) and representatives from TRIO. The SSC will include also a number of study principal Investigators. Other members may be added after consultation with the SSC members. The SSC will be constituted prior to the enrollment of the first patient.

The SSC will have the sole responsibility for the scientific conduct and integrity of the trial. Responsibilities include development and approval of the protocol document, monitoring of accrual, compliance and safety during the conduct of the trial. The SSC will be solely responsible for the analysis, interpretation and public disclosure of the results of the trial in accordance with the statistical plan. The SSC should endeavor to ensure that the study is conducted at all times to the standards set out in Guidelines for Good Clinical Practice (GCP). In all of the deliberations of the SSC, the rights, safety and well being of the study participants are the most important considerations.

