3.1.3. Evaluable Population

The **Evaluable Population** includes all patients who satisfied the following criteria:

- Minimum duration of treatment with darolutamide is 14 days, with a minimum of 10 consecutive days of treatment prior to the definitive surgery.
- Mandatory tumor tissue is collected at screening and at surgery according to the protocol and submitted to the central laboratory.
- Adequacy for molecular assessment of the tumor tissue collected before and after the protocol treatment initiation. The adequacy will be evaluated by the central laboratory.

The evaluable population will be used for the performance of molecular trials and possible hypothesis generation. More information regarding Molecular Analyses will be discussed in a separate document.

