| | AEs assessments | X | X | X | | X |
| | Concomitant medication | X | X | X | | X |
| | Tumor sample | X | | | X | |
| Statistical Methods | 
Up to 60 patients (a minimum of 8 evaluable patients and up to 20 patients in each breast cancer subtype: triple-negative, ER+/HER2 negative, HER2 positive) will be required for the performance of the molecular studies and possible hypothesis generation.
 
A patient will be considered evaluable if the following criteria are met:
 
 Minimum duration of treatment with darolutamide is of 14 days, with a minimum of 10 consecutive days of treatment prior to the definitive surgery. Mandatory tumor tissue is collected at screening and at surgery according to the protocol and submitted to the central lab. | | | | | |

| | |
|--|--|
| | 
 ▪ Adequacy for molecular assessment of the tumor tissue collected before and after the protocol treatment initiation. The adequacy will be evaluated by the central lab. 
Assessment of patient evalability, safety and distribution of patients with respect to hormone receptor status and HER2 status will be performed by the Study Steering Committee (SSC) at given time points depending on the recruitment, primarily planned once 20, around 35 and once all patients have been enrolled and undergone the EoS per protocol. This will allow for the SSC to ascertain that the appropriate number of evaluable patients is being accrued, that more or less patients may be required, or in the extreme case, that accrual should close if the patient evalability rate is very low and/or safety concerns arise.
 
The SSC will define the evalability of patients that discontinue treatment more than 3 days before surgery: molecular analyses may be taken into consideration for the decision about the evalability of such patients.
 
Study Populations
 
 ▪ Intention-to-treat (ITT) Population: the ITT population includes all patients who are enrolled in the study regardless of whether they have been treated or not. ▪ Safety Population: the Safety population includes all subjects who have taken at least one tablet of darolutamide. ▪ Evaluable population: includes all patients who are considered evaluable per protocol. |
|--|--|

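### Protocol 8.5 lets molecular findings help decide which early stoppers enter the primary molecular analysis set

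*Protocol*

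**What the plan says.** Protocol 8.5 sets three criteria for an evaluable patient: enough treatment, mandatory tissue collected at both time points and submitted, and tissue adequate for molecular assessment. On the last of these, "The adequacy will be evaluated by the central laboratory". The section then adds a separate rule for patients who stop drug more than 3 days before surgery or pre-NAST biopsy. The SSC defines their evaluability, and "molecular analyses may be taken into consideration for the decision about the evaliability of such patients". The synopsis carries the same rule.

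Protocol 8.1 defines the evaluable population by the criteria of section 8.5, and section 8.6 states: "The molecular analyses will be performed on the evaluable population". Section 6.5.7.2 makes the comparison of tissue before and after darolutamide the primary endpoint.

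SAP 3.1.3 gives the three criteria, beginning with "Minimum duration of treatment with darolutamide is 14 days, with a minimum of 10 consecutive days of treatment prior to the definitive surgery". It contains no SSC step, and it adds that "More information regarding Molecular Analyses will be discussed in a separate document". The synopses reproduced in SAP Appendices 5.1 and 5.2 do keep the SSC rule; the first reads "The SSC will define the evalability of patients that discontinue treatment more than 3 days before surgery".

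**The concern.** An analysis set should be fixed by facts that do not depend on the outcome. Here the committee may look at molecular analyses before deciding whether a patient counts in the molecular comparison. A patient whose tumour shows no change, or an unwelcome one, could be left out, and one with the expected change kept, after the change is known.

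The same committee controls the results: under Protocol 9.1, "The SSC will be solely responsible for the analysis, interpretation and public disclosure of the results of the trial", subject to the statistical plan. Neither document requires the evaluability decision to be made before results are seen, gives a decision rule, or asks for an analysis with and without these patients.

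The study is uncontrolled and its cohorts are small, so the described pre/post change is its main product. If selection follows the change, the hypotheses the study is meant to generate are distorted.

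**Working it through.** **Chain of definitions**

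1. Protocol 8.5: the SSC decides evaluability for the early-stopping subset and may use molecular analyses.
2. Protocol 8.1: the evaluable population is defined by section 8.5.
3. Protocol 8.6: the molecular analyses are run on that population.
4. Protocol 6.5.7.2: that comparison is the primary endpoint.

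Outcome data can therefore influence membership of the set on which the outcome is described.

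**What the clause may mean.** It does not define molecular analyses. It could be read as baseline or quality-control data only. Two things point to results: adequacy is a separate criterion with a separate assessor, and section 8.6 uses the same term for the pre/post comparison.

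**Size.** The plan gives no figure to reproduce. SAP 2.3 says the cohort numbers did not come from a formal sample size calculation, and neither document gives the number of early stoppers. The following is an illustration.

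Inputs:
- Cohort sizes n = 7, 10 and 19: the enrolled triple-negative, HER2 positive and HR+/HER2 negative counts in SAP 2.3 (7 + 10 + 19 = 36). Evaluable counts may be lower.
- Assumed: one marker, change distributed N(0,1) in SD units, no true change, and k early stoppers in the cohort.
- Assumed worst case: each early stopper is kept only if the marker moves in the expected direction. Each is then kept with probability 1/2, and the mean change among those kept is √(2/π) = 0.798 SD in that direction.

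If j of the k are kept, the cohort mean is 0.798·j/(n − k + j). The expected bias is

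Σ over j of [C(k,j)/2^k] × 0.798·j/(n − k + j).

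Worked cases:
- n = 7, k = 1: ½ × 0.798/7 = 0.057.
- n = 7, k = 2: ½ × 0.798/6 + ¼ × 1.596/7 = 0.0665 + 0.0570 = 0.123.
- n = 10, k = 3: ⅜ × 0.798/8 + ⅜ × 1.596/9 + ⅛ × 2.394/10 = 0.0374 + 0.0665 + 0.0299 = 0.134.

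| n | SE = 1/√n | k = 1 | k = 2 | k = 3 |
|---|---|---|---|---|
| 7 | 0.378 | 0.057 | 0.123 | 0.202 |
| 10 | 0.316 | 0.040 | 0.084 | 0.134 |
| 19 | 0.229 | 0.021 | 0.043 | 0.067 |

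Bias is in SD units, toward the expected direction; k = 0 gives 0. Relative to the standard error, one early stopper of 7 gives 0.057/0.378 = 0.15 and two give 0.123/0.378 = 0.33. Simulation of 200,000 cohorts per case gives 0.059, 0.125 and 0.202 for n = 7, and 0.021, 0.044 and 0.067 for n = 19, in agreement.

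Softer case: an early stopper is kept with probability 0.75 if the change is as expected and 0.25 if not. The chance of being kept is still ½ (½ × 0.75 + ½ × 0.25), and the mean among those kept is (0.75 − 0.25) × 0.798 = 0.399. Every entry halves: 0.03 and 0.06 SD for 1 and 2 of 7, and 0.07 SD for 3 of 10.

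**The case against.** - **The SAP may already remove the discretion.** Protocol 9.1 ties the SSC's analysis role to the statistical plan, and SAP 3.1.3 has no SSC step. But SAP section 1 limits that plan to the secondary objective, its appendices retain the clause, and nothing withdraws it. This supports asking for clarification; it is not a safeguard.
- **A safeguard may sit elsewhere.** The molecular analysis document that SAP 3.1.3 refers to was not available. It could contain a timing rule or a sensitivity analysis. This stands as a limit on the point.
- **Case review has a pharmacological reason.** Protocol 1.2 gives a mean half-life of 11.5 to 16.1 hours. Three days is then 72/16.1 = 4.5 to 72/11.5 = 6.3 half-lives, leaving about 1 to 5% of drug if elimination is first-order. It is reasonable to ask whether such tissue still reflects exposure. Dosing dates and the interval since last intake answer that question without looking at the outcome.
- **The size is small and rests on assumptions.** The protocol names several markers and no expected direction, and treatment normally runs until the day before tissue collection, so such patients may be few. With one per cohort the worst case is 0.02 to 0.06 SD. This stands.
- **Other criteria also involve judgement.** Adequacy is the laboratory's call. That is true, but the text does not tie it to the direction of change.

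**Conclusion.** The concern holds. The protocol contains a stated rule under which outcome information can influence entry to the primary analysis set for patients who stopped more than 3 days before tissue collection. That the clause means post-treatment results is an inference, though the likelier reading. The text shows that such selection is permitted, not that it happened; there is no effect if no such patient exists or the SSC does not use the option.

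Under the assumptions above, the bias is modest in the cohort of 19 and matters most in the triple-negative cohort of seven, where two such patients could shift the mean by up to a third of its standard error. No formal test is planned, so the consequence is a biased description and no error rate is inflated. Separately, SAP 3.1.3 and the SAP's own appendices disagree on whether the SSC step exists and must be reconciled.

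**What to change.** - Remove the permission to consider molecular analyses. State that the SSC judges these patients only from dosing dates, the interval from last intake to tissue collection and the laboratory's adequacy call, with each decision documented before the SSC sees post-treatment molecular results.
- Report the molecular comparison with and without all patients who stopped more than 3 days before tissue collection, and give their number per cohort.
- Put the same rule in SAP 3.1.3 and in the separate molecular analysis document.
- If results have already been seen, report both versions and disclose each SSC decision and what was known when it was made.

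**Cost.** One rule in two documents and one extra descriptive run. The clause is in protocol v3.0 and v5.0 (Germany), so changing the protocol text may need a formal amendment under section 9.4. Enrollment closed on 14 February 2019; the with/without report and the disclosure are the cheapest part and need no new data. The SSC loses discretion over what may be only a few patients.
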